The safety and tolerability of IMG-7289 will be assessed by the analysis of adverse events (AEs), as well as changes in physical examinations, vital signs, and laboratory values as detailed below, using the Safety Population.

A. Exposure

The summary will be presented by disease type (PMF, PPV-MF, and PET-MF) within the starting dose category and include the following:

The summary by patients:

- Summary of patient weekly IMG-7289 dose during initial treatment phase

All exposure data will also be listed by starting dose category, disease type (PMF, PPV-MF, and PET-MF) and patient.

B. Adverse Events

The AEs reported on the eCRFs will be coded using the latest version of MedDRA available to the sponsor at the time of study initiation (up-versioning will not occur), associating lower-level terms with preferred terms and system organ classes (SOC) by the primary hierarchy. The tables will display counts and percentages of patients who reported at least one AE in each system organ class represented in the AE data. Within each system organ class, the tables will

display the counts and percentages of patients reporting at least one AE, as designated by the preferred terms.

In the summary, if a causal relationship is considered probable, possible, or definite by the Investigator, the AE is considered to be “related”; while, if a causal relationship is considered remote/unlikely or unrelated, the AE is considered “unrelated”.

[figure not shown]
Severity of AEs will be reported using the NCI CTCAE grades (v4.03): Grade 1 - Mild, Grade 2 - Moderate, Grade 3 - Severe, Grade 4 - Life-Threatening, and Grade 5 - Fatal.

In any given category (e.g., SOC or preferred term) a patient will be counted only once. If a patient has the same AE on multiple occasions, only the highest toxicity grade will be used. Similarly, only the most related event will be used. For summaries of related events by toxicity grade, if a patient has the same AE with both “related” and “unrelated”, only the highest toxicity grade of the related event will be used. Percentages will be based on the number of patients in the subgroup of patients being tabulated and not the number of events. Summaries that are displayed by system organ class and preferred terms will be ordered by descending order of incidence of system organ class and preferred term within each system organ class.

Sites are intended to document on the AE eCRF those events with an onset date on or after the date on which IMG-7289 was first dispensed, and within 28 days of last IMG-7289 treatment; therefore, all reported AEs are expected to be treatment-emergent. However, if eCRF completion guidelines change, or are not followed adequately, treatment-emergent events will be identified programmatically per the above definition, using imputed start date.

CCI

C. Clinical Laboratory Results

The following laboratory tests will be conducted:

- Complete blood counts (CBC) and differential
- Coagulation
- Chemistry panel including LFTs (AST, ALT, total bilirubin and alkaline phosphatase (ALP)) gamma glutamyltransferase (GGT), albumin , C-reactive protein), lactate dehydrogenase (LDH), uric acid. *Note that C-reactive protein was added starting with amendment 5.*
- Urinalysis with microscopy

Laboratory values will be listed and summarized at each assessment. Numerical laboratory results will be summarized for the actual values, change from baseline (CFB), and percentage CFB by visit; and for the maximum and minimum change from baseline. P-value for test to assess maximum and minimum change from baseline within each cohort will be calculated using paired t-test.

Shift tables for laboratory values with respect to normal range (low, normal, high) and CTCAE toxicity grade, compared to baseline, will be summarized by visit. Overall laboratory result shift from baseline (Normal, Abnormal clinically significant (CS), and Abnormal non-clinically significant (NSC)) will be summarized.

D. Vital Signs

Vital sign assessments will be summarized for the actual values, change from baseline, and percentage change from baseline by visit; and for the maximum and minimum change from baseline. P-value for test to assess maximum and minimum change from baseline within each cohort will be calculated using paired t-test.

E. Physical Examination

Physical exam data will be listed. Note that for Phase 2b patients, a limited version of physical exam data is collected.

F. Prior and Concomitant Medications

Prior medication is defined as any medication with a stop date prior to the date of first dose of IMG-7289. Concomitant medications are defined as medications or therapies with a start date on or after the first dose of IMG-7289. Medications may be flagged as both prior and concomitant if the start date is prior to the date of the first dose of IMG-7289 and the medication continued after the first dose of IMG-7289. The medications will be coded using the most updated version of WHO Drug at the time of study initiation (up-versioning will not occur) and will be listed by cohort and by patient. The number (%) of patients using prior, prior and concomitant, and concomitant medications will be summarized.

G. Prior and Concomitant Transfusions

Prior transfusions are defined as those with a transfusion start date from the 15 days prior to Screening up to the first IMG-7289 dose. Concomitant transfusions are defined as those with a transfusion start date on or after the date of the first IMG-7289 dose. Prior and concomitant transfusions will be listed and summarized.

H. Prior and Concurrent Cancer Chemotherapy

Prior chemotherapy is defined as therapy that has ended before the first IMG-7289 dose. Concurrent cancer chemotherapy is defined as having a cancer chemotherapy start date on or after the date of the first IMG-7289 dose. Prior and concurrent chemotherapy will be listed.

X. Pharmacokinetic Analyses

Pharmacokinetic data are not within the scope of this SAP. Analysis details are provided in the protocol and in a separate Pharmacokinetic Analysis Plan.

XI. References

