#### *Initial Treatment Period (ITP):*

**Note:** Please refer to Section 7.2.3.1 for patients currently being treated under Amendment 5

For patients commencing treatment under Amendment 6, treatment will begin on Day 0 at the new  $D_s$  of 0.6 mg/kg QD. In association with this increased starting dose, the first up-titration is not permitted until Day 28. Extending the time to first up-titration from Day 14 to Day 28 is supported by the observation that the time needed to reach a stable platelet count is between 3 and 4 weeks; additionally, this approach minimizes the risk of severe thrombocytopenia for the few patients who may require less than 0.6 mg/kg/dCCI

[REDACTED]

The platelet titration target expected to be associated with a clinically significant therapeutic effect is:

- A platelet count of  $\geq 50$  to  $\leq 75$  k/ $\mu$ L ( $50-75 \times 10^9/L$ ).

Please refer to Section 7.2.3.2 for additional information on the dosing of Amendment 6 patients.

*Additional Treatment Period (ATP):* Qualifying patients will 're-start' IMG-7289 on ATP Day 0, with dose titration continuing as *per* the Titration Rules in **Table 3**; there should be no interruption in dosing (i.e., Day 168 = Day 0 of new ATP). Additional dose-titration may occur in consultation with the Medical Monitor.

**Study Duration:** CCI

the anticipated duration of participation in the study is expected to be at least 32 weeks from first patient-first visit (FPFV) to last patient-last visit (LPLV). Additional treatment may be given, contingent on an assessment of patient benefit.

**Study Assessments:** The assessments outlined below are presented in detail by study visit in Section 9, and in the Schedule of Assessments Sections 16.1).

The Myeloproliferative Neoplasm Symptom Assessment Form Total Symptom Score (MPN-SAF TSS) will be used. The 24-HOUR RECALL tool (Appendix 16.8) will be completed daily for the 7 days preceding first dose (Days -6 to pre-dose Day 0) during Baseline. The 7-DAY RECALL tool will be completed weekly from Day 7 through the EoS Visit (Appendix 16.9). Multiple questionnaires will need to be provided to patient for completion between visits as visit schedule decreases over time.

Adverse events (AEs) will be assessed at every visit post first IMG-7289 dose through the EoS visit.

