**Table 4: List of Protocol Terms and Meanings**

Term	Protocol Meaning
Limited Physical Exam, including Vital Signs	
 
• Spleen measurement - The edge of the spleen shall be determined by palpation, measured in centimeters, using a soft ruler/tape, from the costal margin to the point of greatest splenic protrusion. The spleen should be measured in the same manner at all visits.
 
• Vital signs, after patient has sat semi-supine for ~3 minutes, of:               
 
○ Heart rate
 
○ Respiratory rate
 
○ Temperature
 
○ Systolic/diastolic blood pressure
 
 
 
• Weight, measured (in kg)
 
• Review of body systems for changes from previous visit
 

Full Local Lab Assessment	Assessment consisting of the following test panels to be performed locally (see Section 10.1.1 for specific analytes required): 
 
• Haematology with manual differential
 
• Coagulation
 
• Biochemistry
 
• Urine or serum pregnancy test for women of child bearing potential (WOCBP); results to be reviewed prior to dosing, if applicable
 

Collect MPN-SAF TSS	MPN-SAF TSS is to be completed by the patient in their native language and in the format provided. The 24-HOUR RECALL tool will be completed daily for the 7 days preceding first dose (Days -6 to pre-dose Day 0) during Baseline. The 7-DAY RECALL tool will be completed weekly from Day 7 through the EoS Visit. Ideally, the 7-DAY RECALL version will be completed on the same time and day each week for consistency. On visit days, the MPN-SAF TSS should be completed prior to the study visit, and if the patient arrives without a completed MPN-SAF TSS, then it will be completed during the visit and collected prior to the patient departing. Importantly, multiple MPN-SAF TSS forms will need to be provided to the patient for completion between visits as visit frequency decreases to less than weekly. Date of completion should be documented on each MPN-SAF TSS completed.

Term	Protocol Meaning

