### 9.2.2 Baseline Period (Days -21 to Day -1) and Enrollment

If Screening and Baseline visits are conducted on separate days, then the following are required at the Baseline visit:

- Limited PE, including vital signs
- Full Local Laboratory Assessment
- Urinalysis

- Germline sample(s) for Central Laboratory genomic analysis
- Blood samples for Central Laboratory genomic analysis\*
- Provide patient with multiple copies of the MPN-SAF TSS **24-HOUR RECALL** tool and instruct patient to complete the questionnaire daily for 7 consecutive days beginning on Day -6 and ending pre-dose Day 0
- Bone Marrow Sampling\*
- Schedule MRI or CT (if patient is not a candidate for MRI) for pre-dose Day 0 ( $\pm 2$  days)

**Note:** In Germany, use of computerised tomography (CT) is not permitted for patients unable to undergo magnetic resonance imaging (MRI). Only MRI is permitted for study purposes.

\*If possible, bone marrow and blood sampling for genomic analysis should be performed on the same day.

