**\*\*24-HOUR RECALL\*\***

**Myeloproliferative Neoplasm Symptom Assessment Form  
 Total Symptom Score (MPN-SAF TSS)**

**Instruction: Completion of this version of the MPN-SAF TSS is required prior to dosing in the IMG-7289-CTP-102 study. It is required *daily* from Day -6 until pre-dose Day 0.**

Symptom	1 to 10 (0 if absent) ranking (1 is most favorable and 10 least favorable)
Please rate your fatigue (weariness, tiredness) by circling the one number that best describes your WORST level of fatigue during the past 24 hours	(No Fatigue) 0 1 2 3 4 5 6 7 8 9 10 (Worst Imaginable)
Circle the one number that describes, during the PAST 24 HOURS, how much difficulty you have had with each of the following symptoms	
Filling up quickly when you eat (Early Satiety)	(Absent) 0 1 2 3 4 5 6 7 8 9 10 (Worst Imaginable)
Abdominal discomfort	(Absent) 0 1 2 3 4 5 6 7 8 9 10 (Worst Imaginable)
Inactivity	(Absent) 0 1 2 3 4 5 6 7 8 9 10 (Worst Imaginable)
Problems with Concentration - Compared to prior to my MPD	(Absent) 0 1 2 3 4 5 6 7 8 9 10 (Worst Imaginable)
Night Sweats	(Absent) 0 1 2 3 4 5 6 7 8 9 10 (Worst Imaginable)
Itching (pruritus)	(Absent) 0 1 2 3 4 5 6 7 8 9 10 (Worst Imaginable)
Bone Pain (diffuse not joint pain or arthritis)	(Absent) 0 1 2 3 4 5 6 7 8 9 10 (Worst Imaginable)
Fever (>100°F / 37°C)	(Absent) 0 1 2 3 4 5 6 7 8 9 10 (Daily)
Unintentional weight loss last 6 months	(Absent) 0 1 2 3 4 5 6 7 8 9 10 (Worst Imaginable)
What is your overall quality of life?	(As good as it can be) 0 1 2 3 4 5 6 7 8 9 10 (As bad as it can be)

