The analyses described in this plan are considered *a priori*, in that they have been defined prior to database lock. If any post-hoc analyses are performed, they will be defined and reported in the CSR.

All analyses will be performed using SAS statistical analysis software version 9.4 or higher of SAS for Windows [SAS Institute Inc; Cary, NC, USA]).

A. Data Sources

All data are collected *via* electronic case report forms (eCRFs) through remote data entry. Section 13.6 of the protocol describes data quality assurance.

B. Definition of Baseline

For analysis purposes, baseline is defined as the last assessment prior to the first dose of study drug. Day 0 is the first day a patient receives study drug. For most measurements, baseline assessments will be taken pre-dose on Initial Treatment Period ITP Day 0. If pre-dose assessments on Day 0 are not available, the most recent prior assessment closest to Day 0 may be substituted in some cases, and unless otherwise specified.

C. Missing Data

For safety and tolerability, missing data, including those not obtained because of death, will be the last value carried forward.

If CTCAE Grade is missing, the event is assumed to be ‘Severe’ (grade 3). If AE relatedness is missing, the event is assumed to be ‘possibly’ related.

When relevant, sections below will address how missing data will be handled for the particular analyses. Otherwise, missing data will not be replaced with imputed values.

D. Display and Imputation Methods for Missing Dates

Every effort will be made to query missing dates. However, partial dates are allowed on the eCRF for Adverse Event (AE) onset and resolution dates (only month and year are required), Concomitant Medication (CM) start and stop dates (only year is required), and Prior and Concurrent Cancer Chemotherapy (PCTHX) start and stop dates (only year is required).

Per protocol, Adverse Events (AEs) are captured in the eCRF commencing with the first dose of IMG-7289 through to the End of Study Visit (scheduled for approximately 28 days post last IMG-7289 dose). For records with missing AE onset day, the following procedure will be employed for use in determining whether the AE is treatment-emergent:

- AE onset dates with missing day will be assumed to occur on the first day of the non-missing month, except for AEs occurring in the first month of dosing, in which case the date will be the first day of dosing.

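### The seven daily baseline symptom forms must start on Day -6, but the visit that first hands them out is allowed up to Day -1; no readable text says how the forms become one baseline score.

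*SAP*

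**What the plan says.** **Protocol, collection.** Table 4 in Section 9 states: "The 24-HOUR RECALL tool will be completed daily for the 7 days preceding first dose (Days -6 to pre-dose Day 0) during Baseline". The synopsis says the same, and the form in Section 16.8 repeats that it is required daily "from Day -6 until pre-dose Day 0".

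**Protocol, hand-out.** When Screening and Baseline fall on separate days, the forms are given out under the section headed "Baseline Period (Days -21 to Day -1) and Enrollment". There the site is told to "instruct patient to complete the questionnaire daily for 7 consecutive days beginning on Day -6 and ending pre-dose Day 0". When the two visits are combined, Section 9.2.1 gives the same instruction at that visit, and Section 9.2 asks only that the visit take place within 21 days before Day 0. No readable text sets a latest hand-out day.

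**SAP, baseline.** Section VI.B gives a general rule: "For analysis purposes, baseline is defined as the last assessment prior to the first dose of study drug". It continues: "For most measurements, baseline assessments will be taken pre-dose on Initial Treatment Period ITP Day 0". If the Day 0 value is missing, "the most recent prior assessment closest to Day 0 may be substituted in some cases, and unless otherwise specified". The only readable SAP text that names symptom scores is VI.J on visit windows. The efficacy text after Spleen Size is blacked out.

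**Use of the score.** Protocol Section 16.7 defines symptoms response as a reduction of at least 50% in TSS and makes it one of three routes to Clinical Improvement. It does not say how seven daily forms become one baseline value.

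**The concern.** A site can follow the visit windows exactly and still be unable to collect the required series, because patients receive the forms after the day on which they should have begun. Patients would then enter the analysis with different numbers of baseline forms for a purely logistical reason, and no readable rule says how many are enough.

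Baseline TSS is the denominator of the 50% criterion. Noise in it moves patients near the cut across the line, and the result carries into Clinical Improvement and, through loss of Clinical Improvement, into relapse as Section 16.7 defines it. If baseline were a single 24-hour form, that noise would be larger than the data already being collected require.

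**Working it through.** **1. Number of forms.** Day -6 to Day 0 inclusive is 7 days, which reproduces the protocol's own figure of seven.

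**2. Visit days that cut the series short.** The Baseline window, Day -21 to Day -1, holds 21 calendar days. Day -21 to Day -6 is 16 days, and a visit on any of them allows all seven forms if the first form may be completed on the visit day. Day -5 to Day -1 is 5 days, and 5/21 = 23.8%.

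| Hand-out visit | Most forms, first form same day | Most forms, first form next day |
|---|---|---|
| Day -7 or earlier | 7 | 7 |
| Day -6 | 7 | 6 |
| Day -5 | 6 | 5 |
| Day -4 | 5 | 4 |
| Day -3 | 4 | 3 |
| Day -2 | 3 | 2 |
| Day -1 | 2 | 1 |

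**3. What the general SAP rule would keep.** Applied literally, it keeps 1 form of 7 and leaves 6 unused. This step holds only if the blacked-out text has no TSS-specific rule.

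**4. Precision.** The documents give no daily SD or correlation, so everything from here rests on assumptions. With equal correlation rho between daily scores, variance of a seven-form mean / variance of one form = (1 + 6·rho)/7. This gives 0.40 at rho 0.3, 0.57 at 0.5, 0.74 at 0.7 and 0.91 at 0.9. If daily errors are independent, their variance falls to 1/7, a reduction of 85.7%.

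**5. Effect on the 50% criterion.** Assume a true TSS of 20 falling to 12 (a 40% fall, so not a response), a follow-up SD of 3, and k independent baseline forms each with daily SD s. Then

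P(false response) = Phi(-(12 - 10)/sqrt(3² + 0.25·s²/k)).

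| Daily SD s | One form | Mean of seven | Difference (points) |
|---|---|---|---|
| 3 | 27.5% | 25.6% | 1.9 |
| 5 | 30.4% | 26.2% | 4.2 |
| 6 | 31.9% | 26.6% | 5.3 |

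An error-free baseline would still give Phi(-2/3) = 25.2%, so most of this misclassification comes from the assumed follow-up error. If daily errors correlate at 0.5, s²/7 becomes s²·(4/7), and the gain shrinks to about 0.9 points (s = 3) and 2.1 points (s = 6).

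A variant with 30 falling to 18 and no follow-up error gives 6.7% against under 0.1% at daily SD 4, and 22.7% against 2.4% at daily SD 8. Because it ignores follow-up error, I do not rest the conclusion on it.

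**The case against.** On the schedule, the best defence is that a deadline is implied: a site told to start patients on Day -6 can comply only by handing the forms out by then. The 9.2.2 heading may also describe a period rather than a list of intended visit days, Section 9.2.4 treats Day -1 only as a reminder contact, and the pre-treatment Schedule of Assessments is not readable. This softens the point but does not remove it. Section 9 calls itself the main guidance for visits and the Schedule merely supportive, and its only stated limits allow a visit on Days -5 to -1. How often that happens cannot be known from the documents.

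On the SAP, a reader might infer that VI.B simply discards six of the seven forms. The documents do not support that. The rule is general, speaks of most measurements and allows for other specification, and any TSS derivation would sit in text that has been blacked out, which does not make it missing.

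A reader might also infer that baseline fails to rest on seven forms whichever rule applies. That too goes too far. If a hidden rule averages the forms, 16 of 21 permitted days still give all seven with a same-day start, and later visits still leave 2 to 6 to average.

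The size is also open to challenge. Section 16.7 requires benefit lasting at least 12 weeks, so a calculation with a single follow-up score does not give the actual false-response rate for the endpoint, in either direction.

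**Conclusion.** The schedule conflict holds on readable text: seven forms from Day -6 are required, while the permitted hand-out can make as few as two possible (one, if the first form is completed the day after the visit). The baseline-rule point holds only conditionally: if VI.B governs the TSS, one of seven forms is used.

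The consequence is modest. Symptom improvement is an exploratory objective that may be analysed only as time and cost allow, the TSS applies to Phase 2b, and no readable primary endpoint uses it. The gain from averaging is about 2 to 5 percentage points in false response, assuming daily SD 3 to 6, follow-up SD 3, independent daily errors and a single follow-up score. It is smaller if daily errors correlate. This is a cheap improvement and does not threaten the trial's main conclusions.

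**What to change.** **Protocol 9.2.1 and 9.2.2.** Hand out the 24-hour-recall forms at Screening, and in every case no later than Day -6 (Day -7 if the first form is to be completed the day after the visit). Naming Screening alone is not enough, because its own window also runs to Day -1.

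**SAP VI.B, unless the blacked-out symptom section already covers it.** Add: For MPN-SAF TSS in Phase 2b, baseline is the mean of the available daily 24-hour-recall forms from Day -6 to pre-dose Day 0, provided at least a prespecified number are present (for example 4 of 7). The 4 is an illustration and has no source in the documents. If the mean is already defined there, add only the minimum number of forms if that is absent.

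**Cost.** One SAP sentence and a change in when a questionnaire is handed out, with no new visit, procedure or data item. The price is a little less scheduling freedom just before Day 0, and a few patients may fall below the minimum. The earlier hand-out cannot help patients already dosed; the averaging rule can still use whatever forms they completed.
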